10.5.2 Exclusion Criteria

Patients assigned to Module 1 must not meet any of the criteria in the core protocol (Section 5.2) and any of the criteria below.

10.5.2.1 Additional Exclusion Criteria for Cohort B1 (R/R MCL)

- 1 Patients with known blastoid or pleiomorphic variant at study entry/most recent relapse.

10.5.2.2 Additional Exclusion Criteria for Cohort B2 (R/R FL or MZL)

- 1 Histologically confirmed diagnosis of FL grade 3B.
- 2 Known transformation to aggressive lymphoma, eg, large cell lymphoma.

10.6 Study Intervention – Module 1

Information related to AZD0466 is provided in Section 6 of the core protocol. The following sections provide information specific to Module 1.

10.6.1 Study Intervention Administration

A description of AZD0466 is provided in Section 6.1 of the core protocol. Dose preparation is detailed in the Handling Instructions supplied to study centres.

10.6.2 Preparation/Handling/Storage/Accountability

Refer to the core protocol (Section 6.2) for a description of AZD0466.

10.6.3 Measures to Minimise Bias: Randomisation and Blinding

Refer to Section [6.3](#) of the core protocol and Module 1-specific information below.

10.6.3.1 Methods for Assigning Treatment Groups

In Module 1 Part A, the actual treatment given to patients will be determined by the sequentially opened cohorts. In Part B, as not all cohorts will be open at a given time, eligible patients can only be allocated to open cohorts. If only one cohort is open, treatment assignment can still occur.

10.6.4 Study Intervention Compliance

Refer to Section [6.4](#) of the core protocol.

10.6.5 Concomitant Therapy

[figure not shown]
Refer to Section [6.5](#) of the core protocol.

10.6.6 Dose Modification and Toxicity Management

10.6.6.1 Starting Dose, Dose Escalation Scheme and Stopping Criteria

The dose escalation part of Module 1 (Part A) will enrol up to approximately ^{CC1} DLT evaluable patients with at least ^{CC1} DLT evaluable patients at each dose level. During Part A, up to ^{CC1} patients may be enrolled per dose level. The structure of the dose escalation part is shown in [Figure 3](#).

Figure 3 **Module 1 Part A Dose Escalation Schema**

^a Alternative dosing schedule: option of dose reduce and/or change in dosing schedule from weekly to every 2 weeks based on emerging safety data.

B-NHL = B-cell non-Hodgkin lymphoma; DL = dose level; MTD = maximum tolerated dose; R/R = relapsed/refractory.

Initial dose levels will be set according to nonclinical modelling and data from Studies D8240C00003 and D8241C00001 with an intra-patient dose ramp-up to mitigate the risk of TLS. The intra-patient ramp-ups will involve beginning at a specified lower dose and rapidly increase the dose to reach target value by Day 8. For example, in dose level 1, at Cycle 1 Day 1 AZD0466 will be administered at 150 mg followed by 300 mg at Cycle 1 Day 4 and reaching target dose of 600 mg at Cycle 1 Day 8. Thereafter, weekly dosing would continue at 600 mg. Each cycle is 28 days with Cycle 1 consisting of ramp-up to achieve the target dose level and then 3 doses at target level on Days 8, 15, and 22 with a 28-day DLT period (see Section 10.6.6.3).

The intra-patient dose escalation scheme and/or dose schedule for each cohort may be modified based on safety, PK, and pharmacodynamic findings of a previous dose level. If a dose level is declared not tolerated due to liver toxicity or cytopenias, the same dose level may be tested at a 2-weekly dosing schedule. Dose escalation from this point will be on a 2-weekly dosing schedule. Should the SRC determine this dose is not tolerated on a 2-weekly dosing schedule, the weekly dose level below will be considered the MTD.

The decisions on the adequacy of the dose escalation portion of the design were based on outcomes from an internal AstraZeneca simulation package which calculates estimates of the likelihood of selecting the true MTD under a range of different scenarios. Operating characteristics are presented in [Table 15](#).

Table 15 Decision Rules Based on mTPI-2 for Dose Escalation

CCI

10.6.6.2 Dose Expansion

Cohorts may open either in parallel or sequentially at the Sponsor's discretion. The dose expansion part of the study (Part B) will enrol up to approximately [redacted] patients. After determining the RP2D in Module 1 Part A (dose escalation), the following separate cohorts may be opened at the RP2D in Module 1 Part B.

- **Cohort B1:** Approximately [redacted] response-evaluable patients with R/R MCL
- **Cohort B2:** Approximately [redacted] response-evaluable patients with R/R FL or MZL
- **Cohort B3:** Approximately [redacted] response-evaluable patients with R/R DLBCL

Following an initial ramp-up during Week 1, AZD0466 will be administered based on a weekly dosing schedule for 2 years or until disease progression, initiation of alternative anticancer therapy, unacceptable toxicity, withdrawal of consent, or other reasons to discontinue study intervention, whichever occurs first. In the event of liver or haematologic toxicities, a 2-weekly dosing schedule may be considered. In the absence of toxicities, a 2-weekly dosing schedule may also be considered after discussion with the Sponsor. For patients who are responding and do not experience unacceptable toxicities, continuation of treatment may be considered by the Investigator and Sponsor.

All patients should be followed for survival every 3 months until death. Patients who discontinue treatment due to unacceptable AEs should be followed until resolution or stabilisation of the AE, then for response and survival. Patients who achieve a CR will be followed for relapse of disease until death.

If the interim analysis of Part B meets the pre-set target value for monotherapy expansion in Cohorts B1 and B2, additional patients will be enrolled in these cohorts.

10.6.6.3 Definition of DLT

A DLT will be defined as the occurrence of any of the following during the 28-day DLT evaluation period in Cycle 1, unless unequivocally due to underlying malignancy or an extraneous cause:

- Haematologic toxicity:
 - CTCAE Grade 3 thrombocytopenia of any duration, associated with Grade ≥ 2 bleeding or requiring platelet transfusion
 - CTCAE Grade 4 thrombocytopenia lasting > 7 days
 - CTCAE Grade 4 anaemia
 - CTCAE Grade 4 neutropenia lasting > 7 days
 - CTCAE Grade ≥ 3 febrile neutropenia (ANC $< 1.0 \times 10^9/L$, fever $> 100.9^{\circ}\text{F}$ [or $> 38.3^{\circ}\text{C}$]) of any duration despite supportive care

- Non-haematologic toxicity:
 - Any CTCAE Grade 3 non-haematologic toxicity lasting > 7 days OR any CTCAE Grade 4 non-haematologic toxicity, with the exception of:
 - CTCAE Grade 4 nausea, vomiting, or diarrhoea lasting < 72 hours in the absence of maximum supportive therapy.
 - Elevation in serum amylase and/or lipase without clinical or radiographic evidence of pancreatitis.
 - CTCAE Grade 3 fatigue, asthenia, fever, anorexia, or constipation.
 - Any other cardiac findings of CTCAE Grade ≥ 2 if considered by the Investigator to be clinically significant. AZD0466 should be permanently discontinued if a CTCAE Grade ≥ 3 cardiac AE of any duration occurs at any time during study intervention, if considered by the Investigator to be related to study intervention.
 - Liver function test abnormalities meeting Hy's Law or potential Hy's Law criteria.
 - Cairo-Bishop Grade ≥ 3 clinical TLS ([Appendix G](#)) that occurs despite protocol-recommended management.
 - Cairo-Bishop Grade ≥ 3 laboratory TLS ([Appendix G](#)) with metabolic abnormalities that do not resolve within 5 days despite protocol-recommended management.
- Any other toxicity that is greater than that at baseline, is clinically significant and/or unacceptable, does not respond to supportive care, results in a disruption of dosing schedule of more than 21 days or is judged to be a DLT by the SRC (toxicity that is clearly and directly related to the primary disease or to another aetiology is excluded from this definition).
- Any CTCAE Grade 5 AEs (please also see Section [4.5](#), study-wide stopping criteria)

Dose-limiting toxicities will not include the following:

- Transient isolated laboratory abnormalities which are not considered clinically significant and resolve to baseline within 72 hours without any intervention.
- Any documented infection, bleeding, or other direct complication of cytopenia due to active underlying disease.

Any event that meets the DLT criteria in the opinion of the Investigator should be reported to the Study Physician within 24 hours of knowledge of the event. Events will be assessed for DLT criteria according to the NCI CTCAE v5.0 except for TLS, which will be assessed for DLT criteria using the Howard et al 2011 modification of Cairo-Bishop 2004 criteria ([Cairo and Bishop 2004](#), [Howard et al 2011](#)).

Any patient who is not evaluable for DLT assessment will be replaced, with the exception of a patient who experiences a DLT; these patients will not be replaced. Additional patients enrolled at a previously cleared dose level to provide supplemental safety, efficacy, PK, and pharmacodynamics data will not be replaced or evaluated for DLT in support of dose escalation decisions. However, these additional patients will be included in the determination of the MTD/RP2D upon completion of the dose escalation part.

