	Cycle 2 and subsequent cycles	
 Consider introducing growth factors (eg, G-CSF), evaluate patient for infection, and begin antibiotic treatment per institutional guidelines Withhold AZD0466 up to 21 days until infection is resolved, and antibiotics are no longer required (except prophylactic antibiotics), and ANC $\geq 1.0 \times 10^9/\text{L}$ 
 On first occurrence, restart AZD0466 at one lower dose (Table 7), after discussion with Study Physician On second occurrence, consider restart AZD0466 at one lower dose than the previous dose (Table 7), after discussion with Study Physician On third occurrence, restart AZD0466 at one lower dose than the previous dose (Table 7), after discussion with Study Physician unless there is no clear evidence of clinical benefit, then consider discontinuing AZD0466

Table 8 Recommended Dose Modifications for Haematologic Toxicities

Toxicity grade	Occurrence	Action
CTCAE Grade \geq 3 thrombocytopenia without the presence of significant bleeding	First occurrence	
 Withhold AZD0466 until values return to CTCAE Grade \leq 1 Restart AZD0466 at one lower dose (Table 7) if values resolve to CTCAE Grade \leq 1 within 14 days Discontinue AZD0466 if the above criteria are not met
	Second occurrence	
 Withhold AZD0466 until values return to CTCAE Grade \leq 1 Restart AZD0466 following the Q2W schedule (Table 6) if values resolve to CTCAE Grade \leq 1 within 14 days Discontinue AZD0466 if the above criteria are not met
	Third occurrence	
 Withhold AZD0466 until values return to CTCAE Grade \leq 1 Restart AZD0466 at one lower dose, maintaining the Q2W schedule (Table 6 and Table 7) if values resolve to CTCAE Grade \leq 1 within 14 days, there is clear evidence of clinical benefit and after discussion with Study Physician Discontinue AZD0466 if the above criteria are not met
	Fourth occurrence	
 Discontinue AZD0466
Presence of significant bleeding events with or without thrombocytopenia, such as: 
 Grade 3 or 4 haemorrhage Any intracranial haemorrhage or haematoma 	Any	
 Maintain platelets at $\geq 50 \times 10^9/L$ until resolution of bleeding Discontinue AZD0466

ANC = absolute neutrophil count; G-CSF = granulocyte colony-stimulating factor; Q2W = every 2 weeks.

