10.6.6.5 Definition of DLT Evaluable Patient

A DLT evaluable patient is defined as a patient enrolled in Module 1 Part A (dose escalation), who has received at least 2 doses of AZD0466 at the target dose level (67% of Cycle 1 after ramp-up) and has completed safety follow-up through the DLT evaluation period, or has experienced a DLT.

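### The DLT list counts Grade 3 thrombocytopenia with bleeding or platelet transfusion, but has no criterion for the same event at Grade 4 lasting 7 days or less

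*Protocol*

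**What the plan says.** The DLT list in Protocol 10.6.6.3, applied over the 28-day window of Cycle 1, has two thrombocytopenia criteria:

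- "CTCAE Grade 3 thrombocytopenia of any duration, associated with Grade ≥ 2 bleeding or requiring platelet transfusion"
- "CTCAE Grade 4 thrombocytopenia lasting > 7 days"

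Elsewhere the plan uses the ≥ sign when it means a grade and everything above it. The same list has "CTCAE Grade ≥ 3 febrile neutropenia" and does likewise for both tumour lysis criteria. Table 8 (6.6.6.2) opens its row on "thrombocytopenia without the presence of significant bleeding" at Grade ≥ 3.

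A bleed can qualify in its own right under the non-haematologic criterion, "Any CTCAE Grade 3 non-haematologic toxicity lasting > 7 days OR any CTCAE Grade 4 non-haematologic toxicity", or as a Grade 5 event. A residual clause covers other toxicity that is worse than baseline: clinically important or unacceptable, refractory to supportive care, causing a dosing gap of more than 21 days, or such that it "is judged to be a DLT by the SRC".

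DLT counts drive the mTPI-2 decisions (Protocol 10.9.2; SAP 10.3.5.2) and the isotonic-regression estimate of the MTD (Protocol 10.6.6.4; SAP 11.1.9.2). The same criteria feed the Part B recruitment-pause rule (Protocol 4.5; SAP 11.1.9.1). SAP 11.1.9.1 refers back to the protocol for the criteria and adds none.

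Under 10.6.6.5, a patient without a DLT is evaluable only after at least two target-level doses and follow-up through the window. Section 10.6.6.3 adds: "Any patient who is not evaluable for DLT assessment will be replaced", except after a DLT.

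**The concern.** The two platelet criteria run the wrong way by severity. A Grade 3 count with Grade 2 bleeding or a transfusion is a DLT whatever its duration. A Grade 4 count with the same bleeding or transfusion is listed only once it has lasted more than 7 days. No reason is given for the difference.

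This toxicity matters for dose finding. Thrombocytopenia is the first important potential risk in Table 1. Section 4.5 calls it an on-target effect and takes it out of the study-wide stopping criteria. In Part A, that leaves the DLT list as its main rule-based control. A short Grade 4 event not classed as a DLT is missing from the escalation decision and the MTD estimate, and the dose chosen goes forward to the Part B cohorts.

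**Working it through.** **Step 1. Classify the events against the two criteria.**

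| Event, with Grade 2 bleeding or a platelet transfusion | Grade 3 criterion | Grade 4 criterion | Listed DLT |
|---|---|---|---|
| Grade 3, any duration | met | not met | yes |
| Grade 4, more than 7 days | not met | met | yes |
| Grade 4, 7 days or less | not met | not met | no |

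The non-haematologic criterion does not close the last row. A Grade 2 bleed never meets it, and a Grade 3 bleed meets it only if it lasts more than 7 days.

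**Step 2. Effect on a dose decision.** There is no plan figure to reproduce: the target rate, equivalence interval, cohort sizes and Table 15 are redacted.

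Inputs from the documents are the beta-binomial model with equal-length intervals (SAP 10.3.5.1), the 95% exclusion rule (SAP 10.3.5.2) and additions usually in threes (Protocol 10.6.6.1). Assumed are targets of 20%, 25%, 30% and 33%, each ± 5 points, a Beta(1,1) prior, and n = 3 or 6.

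The posterior is Beta(1+k, 1+n−k), with distribution function F. Each interval (a, b) scores [F(b) − F(a)]/(b − a), and the highest score sets the decision.

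- *0/3:* the density 4(1−p)³ falls throughout, so the lowest interval wins: Escalate at all four targets.
- *1/3:* F(p) = 6p² − 8p³ + 3p⁴, which gives:

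| Target | Equivalence interval | Next interval up | P(rate > target) | Decision |
|---|---|---|---|---|
| 20% | (0.2617 − 0.1095)/0.10 = 1.522 | (0.4370 − 0.2617)/0.10 = 1.753 | 0.819 | De-escalate |
| 25% | (0.3483 − 0.1808)/0.10 = 1.675 | (0.5248 − 0.3483)/0.10 = 1.765 | 0.738 | De-escalate |
| 30% | (0.4370 − 0.2617)/0.10 = 1.753 | (0.6090 − 0.4370)/0.10 = 1.720 | 0.652 | Stay |
| 33% | (0.4900 − 0.3132)/0.10 = 1.768 | (0.6569 − 0.4900)/0.10 = 1.669 | 0.599 | Stay |

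All four probabilities are below 0.95, so the exclusion rule does not apply. One event left out at n = 3 therefore changes the decision at every assumed target.

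At n = 6, moving from 1/6 to 2/6 changes Escalate to Stay (30%, 33%), Escalate to De-escalate (25%) or Stay to De-escalate (20%). Moving from 0/6 to 1/6 leaves Escalate unchanged at 25%, 30% and 33%.

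**Step 3. Chance of escalating.** At n = 3 escalation needs 0/3. Suppose the true rate of all such events is 40%. If all are counted, the chance is 0.6³ = 0.216. If 10 of the 40 points are unlisted events it is 0.7³ = 0.343, and if 20 points are unlisted it is 0.8³ = 0.512.

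**Step 4. Evaluability.** Target-level doses fall on Days 8, 15 and 22, and two of three (67%) are needed. For a first Grade ≥ 3 event, Table 8 withholds drug, then restarts one dose level lower or discontinues. If that follows the Day 8 dose, no second target-level dose is given and the patient is replaced. If instead the two-weekly option in 6.6.6.1 is used, the next dose falls on Day 8 + 14 = Day 22 at the same level, and the patient stays evaluable.

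**The case against.** The strongest reply is that the event has other ways in.

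- The residual clause names clinically significant or unacceptable toxicity. If its limbs are read as alternatives, Grade 4 platelets with bleeding fit there. So it would be wrong to infer that an SRC vote is the only route.
- Section 4.5 sends thrombocytopenia to the SRC in Part A, and the SRC recommends escalation and sets the RP2D.
- Counts pass through Grade 3, and a transfusion may leave the count there, so the Grade 3 criterion may be met within the same episode.
- Bleeds of Grade 4 or 5, or Grade 3 for more than 7 days, count on their own.

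All of this stands, and it means the event can be missed, not that it must be. But the first two routes rest on judgement, and the protocol does not say how an episode spanning two grades is classified.

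A reader might also infer that the affected patient necessarily leaves the dose-finding data. The documents do not support that. Table 8 is headed as recommended, 6.6.6.1 leaves modification to the Investigator and suggests a two-weekly schedule for platelet changes, and 6.6.6.2 speaks of withholding in subsequent cycles. Replacement is possible, not certain. SAP 5.1.2.2 would also list exclusions with reasons, though not beside the DLT counts.

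The 21-day limb is arguable either way. A hold starting on Day 15 reaches 21 days on Day 36, after the window closes, but the text does not say that the gap must finish inside the window.

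Finally, the footnotes to Table 15 show that some Escalate and De-escalate entries become Stay below a redacted minimum number of patients. If that minimum exceeds three, the n = 3 results do not apply and those for n = 6 are the relevant ones.

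**Conclusion.** The point holds on the wording. A counting rule behind the primary Part A result lists the milder event and omits the more severe one when it lasts 7 days or less. The omission cannot be read as intended shorthand, since the list and Table 8 use ≥ where they mean it and the same criterion uses it for the bleeding grade.

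The gap is confined to one sub-type. It would be too strong to say that thrombocytopenia as a whole is miscounted, or that a dose level with two or three such events in six would be read as 0/6. That would require no other DLT, and none of these events classed as a DLT by any other route.

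The supportable size is this: at n = 3, one uncounted event turns Stay or De-escalate into Escalate at every assumed target from 20% to 33%. At n = 6 the effect depends on the other DLTs. These figures rest on the assumed targets, intervals and prior, and are not the study's own operating characteristics.

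**What to change.** - In Protocol 10.6.6.3, reconcile the two thrombocytopenia criteria so that a more severe event with the same consequences is not treated more leniently than a milder one. The threshold is for the sponsor to choose.
- State how an episode that passes through both grades is classified.
- In Protocol 10.6.6.5 and SAP 11.1.9, require the SRC to rule on DLT status before replacing any patient who missed target-level doses because of related toxicity. Report these patients by dose level beside the DLT table.
- Reconcile 6.6.6.1, the text of 6.6.6.2 and Table 8 on what follows a first platelet event, since evaluability depends on it.

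The cost is a protocol amendment with ethics and regulatory approval (Appendix A 1); the amendment summary classed its last change to the DLT list as substantial. The SAP needs a sentence and an extra table row. A dose level may record a DLT slightly sooner.

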10.6.6.4 Definition of Maximum Tolerated Dose

The MTD evaluation will be based on the DLT evaluable population. The MTD will be determined by isotonic regression analysis applied to DLT rates observed during the dose escalation phase. The estimated MTD will be selected as the dose with the smallest absolute value of difference between the estimated DLT rate and the target DLT rate of **CCI**% among all doses.

If 2 or more doses tie for the smallest difference, the following rules will be applied:

- If the estimated DLT rate is **CCI**% for all doses, then select the higher dose among the tied doses.
- In the case of dose levels with estimated toxicity of equal distance from the target toxicity of **CCI**% (tied dose levels), the following approach will be used ([Ji et al 2010](#)); among all tied dose levels the highest dose level with target toxicity **CCI**% will be selected, unless all tied dose levels have estimated toxicity **CCI**%, in which case the lowest dose level will be selected.
- If the estimated DLT rate for the tied doses are a combination of **CCI**% and **CCI**% then select the higher dose among the tied doses.
- If the estimated DLT rate is **CCI**% for all doses, then select the lower dose among the tied doses.

If the original dose schedule is rejected, the lower tested doses from the original schedule or doses from the revised schedule may be used.

10.6.6.5 Definition of DLT Evaluable Patient

A DLT evaluable patient is defined as a patient enrolled in Module 1 Part A (dose escalation), who has received at least 2 doses of AZD0466 at the target dose level (67% of Cycle 1 after ramp-up) and has completed safety follow-up through the DLT evaluation period, or has experienced a DLT.

10.6.6.6 Dose Escalation Committee

This study will utilise an SRC, as described in [Appendix A 5](#).

10.6.6.7 Dose Modifications

Refer to Section [6.6.6.1](#) of the core protocol for AZD0466 dose modification and toxicity management guidelines.

10.6.6.8 Resumption of Treatment

Refer to Section [6.6.7](#) of the core protocol.

10.7 Discontinuation of Study Intervention and Patient Discontinuation/Withdrawal – Module 1

Refer to Section [7](#) of the core protocol.

10.8 Study Assessments and Procedures – Module 1

10.8.1 Efficacy Assessments

Refer to Section [8.1](#) of the core protocol.

10.8.2 Safety Assessments

10.8.2.1 Physical Examinations

Refer to Section [8.2.1](#) of the core protocol.

10.8.2.2 Vital Signs

Refer to Section [8.2.2](#) of the core protocol.

10.8.2.3 Electrocardiograms

Refer to Section [8.2.3](#) of the core protocol and to the Module 1-specific information below.

Twelve-lead centrally-read digital ECGs will be performed in triplicate, however, if safety ECGs are being collected at a matched timepoint as Holter ECGs (ECGs for PK purpose), single safety ECG is sufficient. If a single safety ECG is abnormal, triplicate safety ECGs are recommended.

Electrocardiograms will be performed at timepoints specified in the SoA and as indicated in [Table 16](#) below.

Table 16 Module 1 Part A and Part B Safety ECG and Holter ECG Extraction

Study period	Day	Timepoint	Holter ECG extraction (for PK) ^a	Triplicate ECG (for safety)
Screening	-28 to -1	Baseline	--	X
Cycle 1	Day 1	Pre-infusion	--	X ^b
		End of the infusion (+ 10 min)	--	X ^b

Table 16 Module 1 Part A and Part B Safety ECG and Holter ECG Extraction

Study period	Day	Timepoint	Holter ECG extraction (for PK) ^a	TriPLICATE ECG (for safety)
	Day 2	24 hours after the start of the Day 1 infusion (\pm 2 hours)	--	X
	Day 4	Pre-infusion	--	X ^b
		End of the infusion (+ 10 min)	--	X ^b
	Day 5	24 hours after the start of the Day 4 infusion (\pm 2 hours)	--	X
	Day 8	Pre-infusion	X	X ^b
		30 min after start of infusion (\pm 5 min)	X	-
		End of the infusion (+ 10 min)	X	X ^b
		2 hours from start of Day 8 infusion (\pm 15 min)	X	-
		6 hours from start of Day 8 infusion (\pm 30 min)	X	-
		9 hours from start of Day 8 infusion (\pm 1 hour)	X	-
	Day 9	24 hours after the start of the Day 8 infusion (\pm 2 hours)	X	X ^b
	Day 15	Pre-infusion	--	X
		End of the infusion (+ 10 min)	--	X
	Day 22	Pre-infusion	--	X
		End of the infusion (+ 10 min)	--	X
Cycle 2	Day 1	Pre-infusion	--	X
		End of the infusion (+ 10 min)	--	X
	Day 8	Pre-infusion	--	X
		End of the infusion (+ 10 min)	--	X
Cycle 4 and beyond	Day 1	Pre-infusion	--	See footnote ^c
		End of the infusion (+ 10 min)	--	See footnote ^c
EoT		--	--	X

^a Patients enrolled in cohorts for which the treatment dose has not been cleared by the SRC in previous AZD0466 clinical studies will require continuous recordings of 12-lead ECGs (Holter device) for PK modelling (see Section 10.8.5.1 for PK assessment timepoints)

^b TriPLICATE ECGs will be collected before the PK sample is taken (see Section 10.8.5.1 for PK assessment timepoints).

^c Beyond Cycle 4 ECGs will be collected on even Cycles only ie, Cycle 4, 6, 8 etc; Day 1: pre-infusion and at the end of the infusion (+10 minutes).

ECG = electrocardiogram; PK = pharmacokinetics; SRC = Safety Review Committee.

Continuous 12-lead ECG Recordings (Holter)

Patients enrolled in cohorts for which the treatment dose has not been cleared by the SRC in previous AZD0466 clinical studies will require continuous recordings of 12-lead ECGs (12-lead Holter devices) for the purpose of PK modelling. When electrocardiogram Holter monitoring is performed, extractions will capture PR, QRS, QT, QTcF, and RR intervals. Recording should be performed as specified in [Table 13](#) of the SoA and [Table 16](#) above, with recording commencing on C1D8 pre-infusion to cover the 24-hour timepoint (prior to PK sampling). The timing of ECGs may be altered depending on the emerging PK profile. The standardised 12-lead Holter device will be provided by the central ECG vendor who will provide the central ECG reads.

The 12-lead Holter devices will always be fitted and safely removed by the Investigator or a trained designee.

The schedule of continuous ECG recordings may be increased, reduced, or stopped at any time during the study, if supported by emerging data and with the agreement of the SRC.

